1.1 Disease Background

Extranodal natural killer (NK)/T-cell lymphomas, nasal type (ENKTL-NT) is a subtype of peripheral T-cell lymphoma (PTCL) with a distinctive geographical distribution. The incidence is higher in Asia than in Europe and America (22% vs. 5% of all the PTCLs) [1]. In 2012, a multi-center analysis of pathological classification of 10002 lymphoma subjects in China showed that ENKTL-NT accounted for 6.6% of all the non-Hodgkin lymphomas (NHLs) and 28.1% of all the PTCLs [2]. The 5-year overall survival rate (OSR) is approximately 32%, and the median overall survival (OS) is around 8 months [3, 4].

The Epstein-Barr virus (EBV) is a known cause and contributing factor to ENKTL-NT. EBV infection is always present in ENKTL-NT cases. Epstein-Barr encoding region (EBER) in situ hybridization (EBV encoded RNA) has become a routine test for pathological diagnosis of ENKTL-NT [1]. Data indicate that positive-EBER and high EBV DNA copy numbers in peripheral blood ($> 6.1 \times 10^7$ copies/mL) are associated with poor PTCL prognosis [5, 6] and high EBV DNA copy number ($> 10^5$ copies/mL) indicates poor treatment efficacy [7]. EBV promotes the development of tumors by activating the STAT1 signaling pathway, inhibiting the TGF β -1 signaling pathway, and up-regulating survivin with EBV nuclear antigen 1 (EBNA1), and the proliferation of tumors by activating NF- κ B and MAPK signaling pathways with latent membrane protein 1 (LMP1) and tumor necrosis factor receptor (TNFR) [8, 9]. Immunotherapy is more suitable for lymphomas associated with EBV, possibly because these tumor cells express more EBV antigens that are recognized by CD8⁺ T-cells [9].

PD-L1 positive expression is detected in approximately 70–75% and PD-1 in approximately 10–30% of all the ENKTL-NT patients. High PD-L1 expression suggests relative good prognosis of PTCL [10–13]. EBV can up-regulate PD-L1 expression on tumor cells, which results in immune tolerance. The main mechanisms are: 1. innate immunity: up-regulation of PD-1 by activating the NF- κ B signaling pathway with LMP1 and continuously activating oncogenic pathways. This mechanism does not rely on inflammatory signals in the tumor microenvironment; 2. adaptive immunity: up-regulation of PD-L1 induced by tumor microenvironment or anti-inflammatory cytokines associated with viral infections such as IFN- γ . In vitro experiments have confirmed that PD-1 monoclonal antibody can restore the activity of T-cells inhibited by diffuse large B-cell lymphoma [14, 15]. In clinical practice, nivolumab has been approved by the US Food and Drug Administration (FDA) for the treatment of Hodgkin lymphoma (HL). High expression of PD-L1 is observed in HL due to the copy number amplification of 9p24.1 (loci for PD-L1, PD-L2, and JAK2 genes) [16, 17]. The above studies provide theoretical bases for the inhibition of the PD-1/PD-L1 axis for the treatment of EBV-associated PTCL.

Anthracycline-based chemotherapies are not used in patients with ENKTL-NT due to the high expression of multidrug-resistant (MDR) P-glycoproteins. The objective response rate (ORR) and complete response (CR) of L- asparaginase- based regimen, SMILE or AspaMetDex, as first-line treatment for ENKTL-NT was 79–80% and 45–66%, respectively [18–20]. However, internationally there is currently no treatment recommendation for ENKTL-NT refractory to L-asparaginase-based regimens. Prognosis is extremely poor in these patients.

High-dose chemotherapy (HDC)/autologous or allogeneic hematopoietic stem cell transplantation (ASCT or HSCT) are currently used as first-line consolidation therapy or second-line salvage therapy. However, there is limited data. Some small sample size reports showed that the subjects with relapsed or refractory ENKTL-NT have a better long-term outcome after HDC/SCT, and sustained response can be achieved for 3–5 years [21, 22]. A retrospective study conducted by the NK-Cell Tumor Study Group showed that 7 of 15 subjects with ENKTL survived and achieved CR after HDT/ASCT [duration of response (DoR): 25+ to 87+ months]. However, 6 of these subjects died within 5 months after the transplantation [23]. Due to the low acceptance of transplant therapy and limited medical resources in China, few patients receive hematopoietic stem cell transplantation. Patients with relapsed or refractory ENKTL in China usually choose to continue with drug treatment.

There is currently no valid prospective clinical data in subjects with ENKTL-NT refractory to L-asparaginase. Guidelines have suggested combination chemotherapy replacing L-asparaginase with pegaspargase for refractory ENKTL-NT may be beneficial [1]. The DeVIC regimen, which is comprised of non-MDR agents, is also recommended in literature[24]. However, this regimen is currently used sequentially after radiation for early ENKTL-NT, and there is no data in advanced, relapsed/refractory ENKTL-NT. The efficacy of gemcitabine for the treatment of PTCL has received attention. Data from a Korean study with small sample size showed that regimens containing gemcitabine achieved an ORR of approximately 40% in subjects with ENKTL-NT, with 20% achieving CR and 20% partial response (PR) [25]. Other drugs such as histone deacetylase inhibitors (HDACi) and anti-CD30 monoclonal antibody have demonstrated efficacy in PTCL but have not been studied in ENKTL-NT treatment. Therefore, there is a significant clinical need to find an effective drug for patients with relapsed or refractory ENKTL-NT.

In Feb. 2017, Yok-Lam Kwong et al. published a small-sample-size study of pembrolizumab for the treatment of 7 subjects with NK/T-cell lymphoma refractory to L-asparaginase regimens in Blood. The ORR was 100%, with 5 cases of CR (71%, among which 2 had undetectable EBV) and 2 cases of PR (29%). The 5 subjects who achieved CR remained in response during a follow-up of 6 months. The treatment was well-tolerated, with only 1 subject developing a grade 2 skin reaction during the study [26]. Compared to other medications, the treatment of relapsed/refractory

NK/T-cell lymphoma with pembrolizumab was characterized by excellent efficacy and mild adverse reactions. On this basis, the investigator will continue to increase the number of subjects and other PTCL subtypes.

In summary, immunotherapy that inhibits the PD-1/PD-L1 axis is very likely to achieve good results in patients with relapsed or refractory ENKTL-NT. This study is thus conducted to evaluate the efficacy and safety of IBI308 in relapsed/refractory ENKTL-NT.

1.2 Investigational Drug (IBI308)

1.2.1 Mechanism of action

Immune checkpoints are a type of immune inhibitory molecules, whose physiological function is to regulate the the immune response, avoiding the damage and destruction of normal tissues. Cancer cells often use these immune checkpoints to avoid being attacked by immune cells. Currently, immune checkpoints CTLA-4 and PD-1/PD-L1 have been validated clinically. Immune checkpoint inhibitors that target PD-1/PD-L1 have better prospects for clinical applications due to better safety and a broader range of indications.

PD-1 is primarily expressed on activated T-cells and has two ligands, PD-L1 and PD-L2. PD-L1 is the main ligand that is expressed on activate T-cells, antigen-presenting cells, and tumor cells[19]. The binding of PD-1 with PD-L1 plays an important role in regulating the activation of T cells and maintaining peripheral immune tolerance. When T cells do not express PD-1, they interact with antigen-presenting cells to enable the activation and proliferation of T cells as well as the activation of cytokine secretion, which can kill the tumor cells. The activated T cells begin to express PD-1. After PD-1 binds to the ligand PD-L1 expressed on the surface of antigen-presenting cells or tumor cells, the inhibitory signal transmitted by PD-1 inhibits the proliferation of T cells and activates the secretion of cytokines, thus weakens the function of T cells. Most tumor cells evade the attack of immune cells through this mechanism. The activity and ability to kill cancer cells of T cells can be restored by blocking the PD-1/PD-L1 interaction with drugs [20].

The US FDA has currently approved 3 PD-1/PD-L1 products, namely, anti-PD-1 antibodies by BMS——nivolumab (brand name: OPDIVO), by Merck——pembrolizumab (brand name: KEYTRUDA), and by Genetech——atezolizumab (brand name: Tecentriq), indicated for advanced melanoma, advanced non-small-cell lung cancer, advanced ENKTL-NT, advanced renal cell carcinoma, urothelial carcinoma, and advanced head and neck cancer. In addition,

many indications have been in phase III clinical studies or have been submitted for approval. The approval of these drugs confirms the important role of PD-1/PD-L1 immune checkpoint inhibitors in cancer immunotherapy. There is no available PD-1/PD-L1 immune checkpoint inhibitors approved for marketing in China. It is of great significance to actively develop such inhibitors to provide better treatment options for domestic patients with advanced cancer.

Recombinant fully human anti-PD-1 monoclonal antibody (R&D code: IBI308) injection is a recombinant fully human IgG4 monoclonal antibody. Multiple preclinical in vitro trials have shown the blockade function of IBI308 of the PD-1 pathway, and the anti-tumor activity of murine analogs of IBI308 has also been indicated in various murine tumor models (refer to the Investigator's Brochure for details regarding study results). The preclinical study results demonstrate the promising use of IBI308 for PD-1 blockade.

1.2.2 Clinical study results

A phase Ia dose-escalation trial was initiated in Sep. 2016. Around 12–24 patients with advanced solid tumors who had failed standard treatment were enrolled. This dose escalation study used the standard "3 + 3" design to evaluate 4 dose levels (1 mg/kg, 3 mg/kg, 200 mg, and 10 mg/kg) of IBI308. After the completion of 1 mg/kg dose administration, subjects were randomized in a 1:1 ratio to either 3 mg/kg or 200 mg arm for independent evaluations. Dose-limiting toxicity (DLT) was observed for 28 days after the first dose for each dose arm. After completion of DLT observation, subjects were treated with IBI308 once Q2W (1 mg/kg, 3 mg/kg, or 10 mg/kg) or Q3W (200 mg) up to 24 months until progressive disease (PD), intolerable toxicity, withdrawal of ICF, or other reasons requiring treatment discontinuation (whichever occurs first).

Pharmacokinetic (PK) evaluation of IBI308 1 mg/kg was conducted in subjects with multiple tumors ($n = 3$). Preliminary results after a single-dose administration showed that IBI308 1 mg/kg reached the maximum drug exposure right after the completion of the single-dose infusion. The drug distribution was rapid after reaching the peak concentration, followed by a slow elimination ($t_{1/2} \approx 17.3$ d), which is the typical two-compartment PK characteristics of a monoclonal antibody. The elimination half-life is similar to the physiological half-life of IgG4.

The pharmacodynamic (PD) results showed that: a dosed of IBI308 1 mg/kg rapidly (24 h) saturated the peripheral PD-1 ($95.8 \pm 2.3\%$) and maintained the receptor occupancy with decreasing concentrations throughout the study (28 d, C28d: 3.70 ± 0.15 $\mu\text{g/mL}$). It is estimated that the steady state can be reached after 84 days with 6 continuous doses of IBI308 1 mg/kg

administered Q2W. If there are no significant changes in drug clearance, the steady-state trough concentration will be around 13 $\mu\text{g/mL}$ and the peripheral PD-1 receptor occupancy will be maintained.

Up to Apr. 16, 2017, the phase Ia study has enrolled 12 patients (3 for each cohort) in 4 treatment cohorts (1 mg/kg, 3 mg/kg, 200 mg, and 10mg), and evaluated the DLTs for each arm. No DLTs were observed. A total of 4 serious adverse events (SAEs) \geq grade 3 were observed in the phase Ia study, among which 3 cases of immune-related pneumonitis and lung infections are possibly related to the investigational drug.

1.3 Risk/Benefit Assessment

Considering the mechanism of action of IBI308 and the clinical safety information of products with similar mechanisms, the main adverse events (AEs) during this clinical trial will possibly be the immune-mediated inflammatory resulted from the activation of immune system, e.g. pneumonitis, colitis, hepatitis, renal insufficiency, and endocrine events. According to the available clinical data, anti-PD-1 monoclonal antibodies are well-tolerated despite of high incidence of adverse reactions. Treatment discontinuation due to adverse reactions only occur in a small number of subjects, and most events resolve after appropriate interventions. Early symptoms of immune-related adverse events (irAEs) vary. Therefore, investigators must closely monitor early signs and symptoms of irAEs during the trial, make correct judgments timely, adjust the dose according to Section 5.4 in the protocol, and provide effective treatment measures to reduce the subject risks. Besides, subjects with autoimmune diseases shall be excluded from the trial to avoid exacerbation of the original disease due to the activation of immune system.

Pharmacological and safety data from the phase Ia clinical trial showed that IBI308 is of clear pharmacological activity and good safety in subjects with advanced cancers.

The preliminary data of the above study show that IBI308 has good pharmacological activity and safety. Since other anti-PD-1 monoclonal antibodies have demonstrated significant efficacy in ENKTL-NT, it is reasonable to conduct a clinical study of IBI308 in Chinese patients with relapsed or refractory ENKTL-NT.

2 Study Objectives

2.1 Primary Objective

- To evaluate the ORR of IBI308 monotherapy for the treatment of relapsed or refractory ENKTL-NT.

2.2 Secondary Objectives

- To evaluate the CR and PR of IBI308 monotherapy for the treatment of relapsed or refractory ENKTL-NT;
- To evaluate the disease control rate (DCR) of IBI308 monotherapy for the treatment of relapsed or refractory ENKTL-NT;
- To evaluate the time to response (TTR) of IBI308 monotherapy for the treatment of relapsed or refractory ENKTL-NT;
- To evaluate the DoR of IBI308 monotherapy for the treatment of relapsed or refractory ENKTL-NT;
- To evaluate the progression-free survival (PFS) and 6-month PFS of IBI308 monotherapy for the treatment of relapsed or refractory ENKTL-NT;
- To evaluate the OS and 6-month OSR of IBI308 monotherapy for the treatment of relapsed or refractory ENKTL-NT;
- To evaluate the safety of IBI308 monotherapy for the treatment of relapsed or refractory ENKTL-NT;
- To evaluate the quality of life of subjects with relapsed or refractory ENKTL-NT after IBI308 monotherapy, using EuroQoL 5 Dimensions 5 Levels (EQ-5D-5L) and European Organization for Research and Treatment of Cancer Quality-of-Life Questionnaire-Core 30 (EORTC QLQ-C30).

2.3 Exploratory Objectives:

- To evaluate the PD-L1 expression and number of tumor-infiltrating lymphocytes (TIL) in tissue samples of subjects with relapsed or refractory ENKTL-NT, RNA expression, dynamic changes in Epstein-Barr virus (EBV) DNA copy number in plasma and peripheral blood lymphocytes, immune cell phenotyping, and association between immune-related cytokines and efficacy of anti-PD-1 treatment.

3 Study Design

3.1 Overall Design

This is a multicenter, single-arm, phase II clinical trial evaluating the efficacy and safety of IBI308 monotherapy for the treatment of relapsed or refractory ENKTL-NT. Patients with relapsed or refractory ENKTL-NT will be enrolled to receive IBI308 200mg IV Q3W up to 24 months until PD, death, intolerable toxicity, withdrawal of ICF, or other reasons stated in the

protocol. For subjects who develop PD for the first time and are clinically stable, the investigator can continue treatment up to 24 months until further PD, death, intolerable toxicity, withdrawal of ICF, or other reasons stated in the protocol.

The primary endpoint is ORR, defined as the proportion of subjects who either experience CR or PR as the best overall response based on imaging evaluation. The primary endpoint will be analyzed after the last statistical and radiological evaluable subject completes a maximum of 24 weeks of follow-up. The tumor assessment is according to Lugano 2014 Criteria (see Appendix 3) and IWG 2007 Criteria after week 24 (see Appendix 4).

The safety follow-up will be performed until 90 days after the last dose.

3.2 Design Principles

3.2.1 Rationale for a single-arm design

It is recommended the DeVIC regimen, which is comprised of non-MDR agents [24], and sequential radiotherapy for the treatment of early ENKTL-NT. There is no data in advanced, relapsed/refractory ENKTL-NT. Data from a Korean study with small sample size showed that regimens containing gemcitabine achieved an ORR of approximately 40% in subjects with ENKTL-NT, with 20% achieving CR and 20% PR [25]. Other drugs such as HDACi and anti-CD30 monoclonal antibody have demonstrated efficacy in PTCL, but have not been used in ENKTL-NT treatment. Therefore, there is a significant clinical need to find an effective drug for patients with relapsed or refractory ENKTL-NT.

In Feb. 2017, Yok-Lam Kwong et al. published a small-sample-size study of pembrolizumab for the treatment of 7 subjects with NK/T-cell lymphoma refractory to L-asparaginase regimens in Blood. The ORR was 100%, with 5 cases of CR (71%, among which 2 had undetectable EBV) and 2 cases of PR (29%). The 5 subjects who achieved CR remained in response during a follow-up of 6 months. The treatment was well-tolerated, with only 1 subject developing a grade 2 skin reaction during the study [34]. Compared to other medications, the treatment of relapsed/refractory NK/T-cell lymphoma with pembrolizumab was characterized by excellent efficacy and mild adverse reactions. The data of the above studies indicate that anti-PD-1 monoclonal antibodies may have significant efficacy in patients with relapsed or refractory ENKTL-NT who have failed multiple lines of treatment and are better tolerated compared to other drugs. A single-arm design will be used because there is no standard treatment for relapsed/refractory ENKTL-NT in China.

3.2.2 Rationale for a treatment regimen of 200 mgQ3W

In this study, IBI308 will be administrated as 200 mg Q3W. This method of administration is used primarily due to the safety and exposure (concentration)-response (PD-1 receptor occupancy) correlation data from the ongoing phase I study (CII308A101) as well as the preclinical in vitro/in vivo PD comparisons with drugs of the same class.

In vivo PD studies involving SCID-Winn mice model and MC38 mice colon cancer model showed that the anti-tumor effect of IBI308 increased with dose, and IBI308 10 mg/kg significantly inhibited cancer growth. The human equivalent dose is 0.8 mg/kg. IBI308 1 mg/kg rapidly (24 h) saturated the peripheral PD-1 ($95.8 \pm 2.3\%$) and maintained the receptor occupancy with decreasing concentrations throughout the study (28d, C28d: $3.70 \pm 0.15 \mu\text{g/mL}$). Tissue distribution of IBI308 in cynomolgus monkeys showed that IBI308 exposure in lungs, liver, colon, small intestine, lymph nodes were 3.5–1/10 of its serum concentration. Given there are no significant changes in drug clearance, it is estimated that steady state can be reached after 84 days with 6 continuous doses of IBI308 200 mg Q3W. The steady-state trough concentration would be around 26 $\mu\text{g/mL}$ and peripheral PD-1 receptor occupancy would still be maintained. The above data support the use of IBI308 200 mg Q3W as the treatment regimen of this study.

3.2.3 Rationale for a primary endpoint analysis after the maximum of 24 weeks

There are currently no large-scale and long-term follow-up clinical trials evaluating PD-1/PD-L1 monoclonal antibodies for the treatment of ENKTL-NT. In the latest small-sample-size study of pembrolizumab for the treatment of 7 subjects with NK/T-cell lymphoma refractory to L-asparaginase regimens, the ORR was 100%, with 5 cases of CR remained in response during a follow-up of 6 months [26]. Therefore, it is expected that most ORR events will be observed if the primary endpoint analysis is conducted after the last subject has completed up to 24 weeks of treatment.

3.2.4 Rationale for choosing ORR as the primary endpoint

There are currently no similar large-scale clinical trials available for reference in China or abroad. The ORR is 40%, CR is approximately 20% [25], and 5-year OSR is around 32% in subjects with relapsed/refractory ENKTL-NT with monotherapy [3, 4]. Therefore, there is a significant clinical need to find an effective drug for patients with ENKTL-NT. There is only one small-sample-size study of pembrolizumab for the treatment of 7 subjects with NK/T-cell lymphoma refractory to L-asparaginase regimens. The ORR was 100%, with 5 cases of CR (71%,

among which 2 had undetectable EBV) and 2 cases of PR (29%). The 5 subjects who achieved CR remained in response during a follow-up of 6 months [26]. Since it is likely that IBI308 will yield similar results in the relapsed/refractory ENKTL subtype, ORR is chosen as the primary endpoint for this study.

3.2.5 Rationale for treatment after PD

Clinical data from approved products showed that a small number of subjects receiving immunotherapy may benefit clinically despite of preliminary evidence of PD (based on routine response criteria) prior to achieving objective response and/or stable disease [27, 28]. This phenomenon can be explained by two possibilities. First, increased inflammation in tumors may lead to increase of tumor volume, manifested as elevated measurable lesions and emergence of new, visible, non-measurable lesions. Over time, the malignant and inflammatory parts of the mass may shrink, resulting in significant imaging response and improvement in clinical signs. Second, in some patients, the initiation of anti-tumor immune response is slow, and tumor inhibition in the early stages is less than the tumor growth. Over time, anti-tumor activity will dominate, giving rise to imaging response and improvement in clinical signs. In Checkmate 205, a reduction in tumor burden after continuing treatment was observed in 6 of 9 cHL subjects with PD [27]. Response after pseudo-progression has also been seen in subjects with renal carcinoma during treatment with immune checkpoint inhibitors [28]. A small--sample-size study conducted at the University of Hong Kong involving pembrolizumab for the treatment of ENKTL-NT also had 1 subject who achieved CR after pseudo-progression [26]. Thus, subjects treated with IBI308 treatment may continue to receive the study treatment after being initially assessed to have PD by the investigator according to the Lugano 2014 Criteria, provided the subject is will benefit clinically and can tolerate the drug (see Section 5.1.2). Subjects must discontinue the study treatment if there are further evidence of PD.

4 Study Population

4.1 Inclusion Criteria

1. Histologically confirmed ENKL-NT.
2. Relapsed or refractory ENKTL-NT. Being relapsed is defined as presence of new lesions at the primary location or other sites after achieving CR; being refractory is defined as any one of the followings: PD after 2 treatment cycles, PR not achieved after 4 treatment cycles, or

CR not achieved after 6 treatment cycles. Patients who do not response or patients with relapsed disease or PD after autologous stem cell transplantation can enroll.

3. Must have been treated with asparaginase-based regimen (radiotherapy must be performed for stage I/II disease).
4. Long axis of a lesion > 15 mm or ¹⁸FDG-PET uptake by lesion.
5. Eastern Cooperative Oncology Group Performance Status (ECOG PS) scores of 0–2.
6. Signed the ICFs and able to comply with the scheduled follow-up visits and related procedures required in the protocol.
7. Between the ages of ≥ 18 to ≤ 70 years.
8. Life expectancy ≥ 12 weeks.
9. Patients (female patients at childbearing age or male patients whose partners are at childbearing age) must take effective contraceptive measures during the entire course of the trial and within 90 days since the last dose of treatment (see Section 4.3).
10. Adequate organs and bone marrow functions, as defined below:
 - Count of whole blood cells: absolute neutrophil count (ANC) $\geq 1.0 \times 10^9/L$, platelets (PLTs) count $\geq 50 \times 10^9/L$, hemoglobin (HGB) ≥ 8.0 g/L; granulocyte colony-stimulating factor, PLT, or red blood cell (RBC) transfusion has not been performed within 7 days prior to the test.
 - Hepatic function: total bilirubin (TBIL) $\leq 1.5 \times$ upper limit of normal (ULN), alanine aminotransferase (ALT) and aspartate aminotransferase (AST) $\leq 2.5 \times$ ULN.
 - Renal function: serum creatinine (Cr) $\leq 1.5 \times$ ULN.
 - Thyroid function: normal thyroid stimulating hormone (TSH) at baseline, or abnormal TSH at baseline with normal T3/T4 and no symptoms.

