- (URBC), and urine glucose (UGLU). The tests will be conducted within 7 days prior to the first dose of the investigational drug, within 3 days prior to the administration of the investigational drug from Cycle 2 onwards, and during safety follow-up. Tests shall be performed at the study sites.
7. Women of childbearing potential shall undergo urine or blood pregnancy test within 3 days prior to the first dose and during the end-of-treatment visit. If the urine pregnancy test is not conclusive, then blood pregnancy test shall be performed. The conclusion shall be based on the blood pregnancy test. Tests shall be performed at the study sites.
 8. T3, T4, free thyrodothronine (FT3), free thyrodothronine (FT4), and TSH shall be tested during screening, prior to the administration of the investigational drug from Cycle 2 onwards, and during safety follow-up. Tests shall be performed at the study sites.
 9. Immunogenicity assays will be carried out within 1 hour prior to IBI308 administration in Cycles 1, 2, 4 and then every 4 cycles thereafter (Cycle 8, 12, 16, and so on), and during safety follow-up. Tests shall be conducted at the central laboratory.
 10. EBV DNA shall be tested on the day of IBI308 administration in each cycle, with 4 mL of blood collected each time, until the end of study treatment. Tests shall be conducted at the central laboratory. According to the changes of patients' condition and the needs of efficacy evaluation, EBV DNA test may be added by investigators at the centre.
 11. Hepatitis B panel (HBsAg, HBsAB, HBcAB, HBeAg, and HBeAb), HCV antibody, and HIV antibody will be tested during screening. If the result shows HBsAg positive, then HBV DNA test shall be further conducted; if the result shows HCV antibody positive, then HCV RNA test shall be further conducted. For HBV DNA-positive subjects or HBV carriers, HBV activity shall be monitored regularly, and prophylactic antiviral therapy is suggested to be performed according to the treatment guidelines for chronic hepatitis B during the trial. Tests shall be performed at the study sites.
 12. AE and laboratory safety evaluation are performed according to NCI CTCAE v4.03. Refer to Section 7 for AE and SAE definitions, recording, determination of causal relationship, severity, reporting deadlines, and processing.

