Alternative Version 2 to Version 1 (Version Date:May.11, 2017)

Main change	Description
1. Sample sizes changed from minimum of 60 patients to 20-60 patients	When 28 patients were enrolled, several early PD were observed, and the Lugano 2014 criteria made response evaluation difficult due to the lack of a definition for pseudo-progression. Therefore, enrollment was paused, but treatment was continued to confirm the true nature of the pseudo-progression according to investigator's discretion. After 3 months of observation and in-depth analysis of the 28 patients, sintilimab demonstrated 67.9% ORR when taking pseudo-progression into consideration. Planned total enrollment was not reached. When hypothesizing that the 15 yet-to-be-enrolled patients would be non-responders, there would be 19 responders out of 43 (28 actually enrolled + 15 fictive), providing a 95% CI by Wilson's method of 30.4%-58.9%, where the lower boundary is still greater than the pre-planned 30% threshold. There's no need to enroll a total of 60 patients.
2. Add RNA expression as a biomarker	Detection of RNA expression could help to capture potential biomarker for predicting response.
3. Modify the treatment duration up to 24 months	No clinical benefit evidence to support a long treatment duration for more than 2 years.
4. Modify the final injection volume (after preparation) from 250 ml to 100 ml	Based on the updated stability test of sintilimab, the recommended final concentration is 1.5~2 mg/ml.
5. Remove the second interim analysis	There no need to perform a second interim analysis.

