### **Protocol Deviations**

Summary will be provided for number and percentage of subjects with major protocol deviation. Listing will be provided for subjects with major protocol deviation and inclusion/exclusion criteria deviation.

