### 5.6.2 Clinical Laboratory Evaluation

Clinical laboratory evaluation includes hematological exam, blood chemistry, urine test. Local lab is used in this study and results will be analyzed and reported using international standard unit. Invalid results if marked will not be included in the analysis. Non-protocol specified laboratory test or test out of study center will not be included in the summary analysis. If abnormal is observed, AE will be reported.

Laboratory results will be summarized as normal, abnormal low, abnormal high according to normal range of each center. Abnormal values will also be reported by investigators as clinically significant or not. If “<”, “<=”, “>” or “>=” limit of quantitation, limit of quantitation will be used for summary statistics. Original results will be displayed in listing.

In SS, by visit descriptive summary will be provided for quantitative clinical laboratory evaluation. For qualitative evaluations, shift summary of change from baseline will be provided based on normal/abnormal status and clinically significant/not clinically significant status.

Listing will be provided for clinical laboratory evaluation results. Virology and (or) pregnancy exam will be listed separately.

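### The hemoglobin entry limit is printed as 8.0 g/L (0.8 g/dL) in both the synopsis and section 4.1, so it excludes no realistic candidate

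*Protocol*

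**What the plan says.** Criterion 10 opens with "Adequate organs and bone marrow functions, as defined below" and then lists laboratory limits. Its blood-count bullet asks for neutrophils of at least 1.0 × 10⁹/L, platelets of at least 50 × 10⁹/L, and "hemoglobin (HGB) ≥ 8.0 g/L". The synopsis and section 4.1 give the same number and unit. The bullet ends with a washout for growth factor and transfusion, including the condition that "red blood cell (RBC) transfusion has not been performed within 7 days prior to the test".

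Criterion 5 in the same list requires "Eastern Cooperative Oncology Group Performance Status (ECOG PS) scores of 0–2", and criterion 8 requires a life expectancy of at least 12 weeks.

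On when hemoglobin is measured, note 6 to Table 1 of the protocol says "The tests will be conducted within 7 days prior to the first dose of the investigational drug". On its use in the analysis, SAP section 5.6.2 says that "results will be analyzed and reported using international standard unit", and the Protocol Deviations part of SAP section 5.2 says "Listing will be provided for subjects with major protocol deviation and inclusion/exclusion criteria deviation".

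The Summary of Amendment at the end of the protocol gives the number already entered: "When 28 patients were enrolled, several early PD were observed". It does not mention the hemoglobin limit.

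**The concern.** A limit of 8.0 g/L is 0.8 g/dL. A criterion meant to secure adequate marrow function therefore has one component that every candidate passes. The transfusion washout in the same bullet shows that the limit was meant to bind: barring a recent red-cell transfusion serves little purpose if the hemoglobin value it protects can never fail.

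There are two consequences.

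- **Safety at entry.** This is the only numeric hemoglobin requirement for entry. As printed, a severely anemic patient satisfies it.
- **Deviation reporting.** The SAP promises a listing of eligibility deviations. If hemoglobin is stored in g/L and the check is taken literally from the criterion, each value is compared with 8.0 and no anemic subject is listed. The documents do not say how the listing is derived, so this is a possibility to rule out and not an established fault.

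**Working it through.** The plan derives no figure here. The check is a unit conversion, a search for any other limit that would rescue the criterion, and an illustration.

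**Inputs from the documents**

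- Printed limit: 8.0 g/L (protocol synopsis and section 4.1, criterion 10).
- Enrolled subjects: 28 (Summary of Amendment).
- Permitted enrollment: 20 to 60 (protocol section 8.5).

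**Conversion** (g/dL = g/L ÷ 10)

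- Printed limit: 8.0 ÷ 10 = 0.8 g/dL.
- If 8.0 g/dL was intended: 8.0 × 10 = 80 g/L.
- Ratio of intended to printed: 80 ÷ 8.0 = 10.
- Range wrongly admitted: 80 − 8.0 = 72 g/L.
- The intended value is not in the documents. For an assumed intended limit of 70 to 100 g/L, the range wrongly admitted is 70 − 8.0 = 62 to 100 − 8.0 = 92 g/L.

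**Other places that might restore the limit**

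| Place | What it provides | Hemoglobin number? |
|---|---|---|
| Protocol 4.2, exclusion 17, last bullet | Investigator may judge a patient ineligible because of a laboratory abnormality | No |
| Protocol 5.3.1 | Hematologic function must be acceptable before each dose; toxicities back to grade 0–1 or baseline | No |
| Protocol 6.1.1 | Sponsor's medical manager must confirm eligibility before enrollment | No |
| SAP 5.6.2 | Reporting of laboratory results | No |

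None supplies a threshold.

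**Illustration.** The documents give no hemoglobin distribution, so the means and standard deviations below are assumptions. With a normal distribution, the share of candidates below a limit x is Φ((x − mean) ÷ SD).

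| Assumed mean / SD (g/L) | Below 8 g/L | Below 80 g/L |
|---|---|---|
| 90 / 15 | Φ(−5.47) = 2.3 × 10⁻⁸ | Φ(−0.67) = 25% |
| 100 / 15 | Φ(−6.13) = 4.3 × 10⁻¹⁰ | Φ(−1.33) = 9.1% |
| 110 / 18 | Φ(−5.67) = 7.3 × 10⁻⁹ | Φ(−1.67) = 4.8% |
| 120 / 15 | Φ(−7.47) = 4.1 × 10⁻¹⁴ | Φ(−2.67) = 0.4% |

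Under these assumptions an 80 g/L limit would exclude between 0.4% and 25% of candidates, while the printed limit would exclude fewer than 3 in 100 million. This shows only that the printed limit is inert. It does not estimate how many of the 28 were affected, which may be none.

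**Effect on the primary analysis.** The full analysis set requires at least one dose and measurable disease, with confirmation of the diagnosis on central pathology. It has no laboratory condition. The test against a 30% response rate and the sample size of 43 do not depend on hemoglobin. The SAP excludes from the per-protocol set subjects who fail major eligibility criteria, but neither document names hemoglobin as one, so no effect on that set is claimed.

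**The case against.** The strongest reply is that the slip corrects itself. An oncologist would not read 8.0 g/L literally, and the more absurd the figure, the less likely it misled anyone. Sponsor review under section 6.1.1 is also a mandatory step for every subject, and exclusion 17 expressly reaches laboratory abnormalities that raise drug-related risk. Neither document describes an automated hemoglobin check, so the reporting consequence is conjecture. With 28 enrolled and the amendment seeing no need to reach 60, correcting the text may protect few or no further patients.

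Much of this stands. Sites may well have applied the intended value, nothing in the documents shows that a severely anemic patient entered, and the literal-check route is conditional. The size of the gap measures the misprint and not its effect on the trial.

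It does not remove the point. The sponsor's review is compulsory, but without a usable number its outcome rests on judgment. The enrollment-error procedure in section 6.1.2 is triggered by an ineligible subject, and on the printed text no anemic subject is ineligible on hemoglobin. The current protocol still permits up to 60 subjects, so the criterion remains in force.

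**Conclusion.** The concern holds. The hemoglobin limit is wrong as written in both places and nothing elsewhere corrects it. The same number and unit in two separate places make a text-extraction fault unlikely. That no realistic candidate falls below 8 g/L is a clinical inference, but a safe one given the performance-status and life-expectancy requirements.

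The error is a factor of 10 if 8.0 g/dL was intended, and that intended value is an assumption. Only the hemoglobin component fails; the neutrophil, platelet, transfusion, hepatic, renal and thyroid conditions still operate. It should be fixed because it is an operative safety threshold, not because it threatens the primary result.

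**What to change.** 1. The sponsor confirms the intended hemoglobin limit.
2. If it is 8.0 g/dL, print it as HGB ≥ 80 g/L (8.0 g/dL) in the synopsis and in section 4.1. Giving both units prevents a repeat.
3. Confirm that any eCRF edit check and the SAP listing of eligibility deviations use that value and unit.
4. Compare the baseline hemoglobin of the 28 enrolled subjects with the corrected limit and list anyone below it, noting that the printed text admitted them.

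The cost is one line in two places, with the ethics committee submission that section 11.3 requires for a protocol change, and a single look at 28 values that the protocol already requires before the first dose. No change to the statistical design or analysis follows.
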